5.1. Co-Primary Efficacy Endpoints

- Proportion of subjects with an IGA success (defined as an IGA of 0 [clear] or 1 [almost clear] and a ≥ 2 -point reduction from Baseline) at Week 16
- Proportion of subjects with EASI-75 ($\geq 75\%$ improvement in EASI from Baseline) at Week 16

5.2. Key Secondary Efficacy Endpoints

- Proportion of subjects with an improvement of PP NRS ≥ 4 at Week 16
- Proportion of subjects with PP NRS < 2 at Week 16

CCI

This document is confidential.

CCI

1.0

CD14152.SPR118169.SAP.V01

Approved 10-Nov-2022 00:00:00

This document is confidential.

CCI

1.0

CD14152.SPR118169.SAP.V01

[figure not shown]
Approved 10-Nov-2022 00:00:00

This document is confidential.

1.0

[figure not shown]
CD14152.SPR118169.SAP.V01

Approved 10-Nov-2022 00:00:00

5.5. Safety Endpoints

- Incidence and severity of AEs, including AESIs, TEAEs, and SAEs
- Physical examination and Vital signs
- Clinical laboratory tests
- Electrocardiogram
- Peak expiratory flow
- Asthma Control Test (ACT)

This document is confidential.

6. Analysis Sets

For Initial Period and Maintenance Period, the following populations will be defined for analysis. Only subjects who are re-randomized after Initial Period will be included in the analysis population of Maintenance Period.

6.1. Intent-to-Treat Population

The intent-to-treat (ITT) population will consist of all randomized subjects. All primary and secondary efficacy endpoints will be analyzed based on the ITT population.

For maintenance Period, the ITT population will include subjects who are re-randomized after Initial Period.

The ITT population will be the primary population for all efficacy analyses. All analyses on the ITT population will be analyzed under the treatment group 'as randomized'. If a subject is stratified incorrectly, 'stratum at the randomization' will be used rather than 'actual stratum' for analysis or summary of efficacy data.

6.2. Enrolled Subjects in Maintenance Period Population

The enrolled subjects in maintenance period population will comprise all subjects in ITT Population who are re-randomized or continue on Placebo after initial period.

6.3. Safety Population

The safety population will comprise all subjects in ITT population who receive at least 1 dose of study drug. All safety data will be summarized based on the safety population under the treatment group 'as treated'.

For Maintenance Period, only subjects in ITT population who received at least one drug in the Maintenance Period will be included in the population.

Subject who are treated on error during the course of the study will be assigned to actual treatment as described below.

Initial Period:

- Subjects who are randomized to Placebo but treated at least once with Nemolizumab in error will be assigned to 'Nemolizumab Q4W'.
- Subjects who are randomized to Nemolizumab but treated at least once with Placebo in error will still be assigned to 'Nemolizumab Q4W'. If they always received Placebo in error during the period, then they will be assigned to 'Placebo'.

Maintenance Period:

- Subjects who are re-randomized to Nemolizumab Q4W but treated at least once with Placebo in error will be assigned to 'Nemolizumab Q4W to Q4W'.
- In case of subjects who re-randomized to Nemolizumab Q8W, they are supposed to receive Nemolizumab and Placebo alternately. If they are treated with Nemolizumab instead of Placebo at least once in error, they will be assigned to 'Nemolizumab Q4W to Q4W'. However if they are treated at least once with Placebo instead of Nemolizumab in error will be assigned to 'Nemolizumab Q4W to Q8W'.

This document is confidential.

- Subjects who are re-randomized to Placebo but treated with Nemolizumab at least once in error will be assigned to 'Nemolizumab Q4W to Q4W'.
- Subjects who are randomized to Placebo for Initial Period and continue the Maintenance Period will be assigned to 'Placebo' even if treated with Nemolizumab at least once in error.

Overall Period:

- If subjects exited the study after Initial Period (i.e., not re-randomized nor continued with Placebo for Maintenance Period), overall period treatment group will be the same with Initial period treatment group assigned (i.e., can be either 'Nemolizumab Q4W' or 'Placebo').
- In case subjects who re-randomized for Maintenance Period,
 - Subjects who are re-randomized to Nemolizumab Q4W will be assigned to 'Nemolizumab Q4W' even if they treated by Placebo in error during the study.
 - Subjects who are re-randomized to Nemolizumab Q8W will be assigned to 'Nemolizumab Q4W to Q8W' if the error occurred during Initial Period. When the error is occurred during Maintenance Period, overall period treatment group will be 'Nemolizumab Q4W to Q8W' if receive Placebo instead of Nemolizumab or 'Nemolizumab Q4W' if receive Nemolizumab instead of Placebo during Maintenance Period.
 - Subjects who are re-randomized to Placebo will be assigned to 'Nemolizumab Q4W to Placebo' if the error is occurred in Initial Period. However if the error is occurred during Maintenance Period, the overall treatment group will be 'Nemolizumab Q4W'.
- Subjects who are randomized to Placebo for Initial Period and continue the Maintenance Period will be assigned to 'Placebo'.

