##### 10.1.1.2 Safety Population

The safety population will comprise all subjects in ITT population who receive at least 1 dose of study drug. All safety data will be summarized based on the safety population under the treatment group ‘as treated’.

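### SAP 6.3 leaves placebo continuers who receive nemolizumab in error under Placebo, contrary to its own as-treated rule

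*SAP*

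**What the plan says.** Protocol 10.1.1.2 and SAP 6.3 both report safety under the treatment actually received. The protocol wording is "All safety data will be summarized based on the safety population under the treatment group" as treated, with no exception. SAP 6.3 adds that subjects treated in error "will be assigned to actual treatment as described below", and then gives rules by period.

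- **Initial Period.** "Subjects who are randomized to Placebo but treated at least once with Nemolizumab in error will be assigned to" Nemolizumab Q4W.
- **Maintenance Period, group 1C.** "Subjects who are re-randomized to Placebo but treated with Nemolizumab at least once in error will be assigned to" Nemolizumab Q4W to Q4W. A Q8W subject given nemolizumab at a placebo visit goes to the same group.
- **Maintenance Period, group 2 continuers.** They are assigned to Placebo "even if treated with Nemolizumab at least once in error".
- **Overall Period.** A subject who exits after the Initial Period keeps the Initial Period assignment. Q8W and 1C subjects given extra nemolizumab in maintenance become Nemolizumab Q4W. Group 2 continuers are Placebo, with no condition attached.

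The SAP gives no reason for treating continuers differently. Section 15, which lists changes from the protocol, mentions only the definition of concomitant medication.

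**The concern.** The other rules for nemolizumab given in place of placebo follow one principle: any nemolizumab exposure in the period counts as nemolizumab. The continuer bullets reverse it for one group. A subject in that group can have an adverse event after a nemolizumab dose and have it tabulated under Placebo.

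The Overall Period bullet is the harder one to defend. Whether a subject continues depends on response at Week 16, which is observed after randomisation and after the erroneous dose. Under this bullet that response decides the safety label of subjects with the same exposure. It also allows one person to be nemolizumab in the Initial Period tables and placebo in the Overall Period tables.

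The exposure is not momentary, since the protocol equates 12 weeks after the last injection with about five half-lives. The PK population (SAP 6.5) is drawn from the safety population and is also analysed as treated, with no mis-dosing rule of its own, so the same labels could carry into the PK and anti-drug-antibody summaries.

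**Working it through.** **1. The rules side by side.** These are the cells of SAP 6.3 in which nemolizumab is received where placebo was due.

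| Period | Subject and error | Group assigned by SAP 6.3 | Moved? |
|---|---|---|---|
| Initial | Placebo subject given nemolizumab | Nemolizumab Q4W | Yes |
| Maintenance | Q8W subject given nemolizumab at a placebo visit | Nemolizumab Q4W to Q4W | Yes |
| Maintenance | 1C subject given nemolizumab | Nemolizumab Q4W to Q4W | Yes |
| Maintenance | Group 2 continuer given nemolizumab | Placebo | No |
| Overall | Q8W subject, error in maintenance | Nemolizumab Q4W | Yes |
| Overall | 1C subject, error in maintenance | Nemolizumab Q4W | Yes |
| Overall | Group 2 continuer, error in either period | Placebo | No |

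Five cells move the subject and two do not. Both of the latter concern group 2 continuers.

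**2. Two subjects with the same error.** Take two subjects randomised to placebo, each given one nemolizumab dose in error before Week 16.

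- Both are Nemolizumab Q4W in the Initial Period tables.
- The one who exits keeps that label and is Nemolizumab Q4W in the Overall Period tables.
- The one who responds and continues is Placebo in the Overall Period tables.

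**3. Size.** Inputs: 750 subjects at 2:1, so 750 × 2/3 = 500 nemolizumab and 750 × 1/3 = 250 placebo; 15% dropout; responder rates of 45% and 12% (Protocol 8.1).

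The plan's maintenance numbers, as N × (1 − dropout) × responder rate:

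- Nemolizumab: 500 × 0.85 × 0.45 = 191.25 (plan: 190).
- Placebo: 250 × 0.85 × 0.12 = 25.5 (plan: 26).
- Total: 191.25 + 25.5 = 216.75 (plan: about 216).

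The plan's figures are reproduced to rounding. The weight of one misplaced subject is then:

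- Maintenance continuers: 1/26 = 3.8%.
- Overall Period Placebo group: 1/250 = 0.4%. SAP 13.1 puts into that group everyone who received placebo in the Initial Period, whether or not they continued.

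The documents give no expected number of dosing errors, so no total effect can be calculated.

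**The case against.** The exception is worded as a deliberate choice, and a practical reason can be guessed. The active maintenance labels, Q4W to Q4W and Q4W to Q8W, both imply nemolizumab in the Initial Period, which a correctly dosed group 2 subject never had. A continuer with one erroneous dose among 12 dosing visits (4 initial, 8 maintenance) has mostly received placebo, and moving the whole subject also moves events that preceded the error. Syringes are assigned by the interactive response system, so errors should be few. Individual events stay traceable in the dosing, deviation and adverse event listings.

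The point about labels stands: an existing active maintenance label cannot simply be applied. The mostly-placebo argument does not stand, because a 1C subject with one active dose among eight maintenance injections is moved. The loss of pre-error events is real, but the SAP already accepts it under its other reassignment rules.

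Two stronger readings are tempting, and the documents do not support them.

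- **That continuers are handled differently from all other mis-dosed subjects.** Nemolizumab subjects given placebo in some visits keep their nemolizumab group, which fits the any-exposure principle. Labels can also differ between period and Overall tables for others. For example, a nemolizumab subject given only placebo in the Initial Period is Placebo in those tables but Nemolizumab Q4W overall if later re-randomised to Q4W. That error runs in the opposite direction and does not excuse the asymmetry, but it shows that a change of label is not peculiar to continuers.
- **That the randomised safety comparison is diluted.** The Initial Period tables already use the any-exposure rule. The randomised placebo contrast in maintenance is 1A and 1B against 1C. Continuers are a non-randomised group of placebo responders shown in descriptive summaries, with no safety hypothesis test.

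**Conclusion.** The inconsistency is real and is written into SAP 6.3. It departs from that section's own as-treated principle and from Protocol 10.1.1.2, without a stated reason. It is confined to group 2 continuers who receive nemolizumab, in the Maintenance and Overall Period summaries. The percentages above rest on the planned enrolment, dropout and response rates, and on essentially all randomised placebo subjects being treated. Because the number of errors is unknown and probably small, this is a minor correction. Efficacy is analysed as randomised and does not change.

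**What to change.** Amend the two continuer bullets in SAP 6.3 before unblinding, so that the assignment cannot appear to depend on outcome. For a continuer with at least one nemolizumab dose in either period:

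- **Overall Period:** assign to Nemolizumab Q4W, which matches the treatment of a mis-dosed placebo subject who exits.
- **Maintenance Period:** remove from Placebo and show under a separately named category, for example Placebo to Nemolizumab (dosed in error), or list separately with a footnote.

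If the sponsor prefers to keep the exception, the SAP should at least state the reason and record it in section 15 as a departure from the protocol. That would explain the inconsistency but not remove it.

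The cost is a wording change and one extra label or footnote, with no new data. The downside is that a subject's pre-error placebo events move with them.

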6.4. Enrolled Safety Subjects in Maintenance Period Population

The enrolled safety subjects in maintenance period population will comprise only subjects in enrolled subjects in maintenance period population who received at least one drug in the maintenance period.

6.5. PK Analysis Population

The PK analysis population will include all subjects in the safety population who provide at least 1 post-Baseline evaluable drug concentration value and not include any biologically implausible value.

For Maintenance Period, only subjects in the safety population who provide at least 1 post-Week 16 evaluable drug concentration and not include any biologically implausible value in the Maintenance Period will be included in the population.

All PK and ADA endpoints will be analyzed using the PK analysis population under the treatment group 'as treated'.

6.6. Enrolled PK Subjects in Maintenance Period Population

The enrolled PK subjects in maintenance period population will comprise only subjects in enrolled Safety subject in maintenance period population who provide at least 1 post-week 16 evaluable drug concentration value and not include any biologically implausible value.

6.7. Per-Protocol Population

The per-protocol (PP) population will comprise all subjects in the ITT population who have no major protocol deviations that would have a significant effect on the efficacy of the study treatment. Only

This document is confidential.

primary and key secondary endpoints will be analyzed using the per-protocol population under the treatment group 'as randomized'.

6.8. PD Analysis Population

The PD analysis population(s) will be described in a separate pharmacodynamic plan by designated CRO.

6.9. Protocol Deviations

Protocol deviations will be recorded by the Clinical Research Associate (CRA) in the Clinical Trial Management System (CTMS). All protocol deviations will be categorized by deviation type which the deviation is associated with, and will be assessed individually on a regular basis on whether they are important (major) or non-important (minor). Details can be found in the Protocol Deviation and Non-compliance Management Plan.

Major protocol deviations would lead to an exclusion of the subject from the per-protocol population. A case by case decision regarding exclusions of subjects from the per-protocol population will be made in a blind data review meeting (BDRM) which will take place prior to unblinding the study.

Individual deviations (major and minor) will be presented in a data listing on the ITT population. A summary table for number and percentage of subjects with major protocol deviation will be summarized by type of deviation and treatment group for the Initial Period and the Maintenance Period for the ITT population.

Protocol deviations incurred as a direct result of the COVID-19 pandemic should be specifically recorded and presented as a COVID-19 deviation. The number and percentage of subjects with major COVID-19 deviation will be provided by type of deviation and treatment group for the Initial Period and the Maintenance Period for the ITT population.

Major protocol deviations will also be summarized by site for the ITT population.

This document is confidential.

[figure not shown]
7. Estimands

The co-primary and key secondary efficacy endpoints will be evaluated in the moderate-to-severe atopic dermatitis represented by the study inclusion/exclusion criteria and assigned to treatment during initial period. The estimand is defined to address the scientific question relevant to subjects who are able to complete treatment with a response assessment without further medication being required, other than the allowed background and rescue medication.

An intercurrent event is an event which occurs after start of treatment and thus complicates the description and interpretation of treatment effects. Table 7-1 below lists potential intercurrent events and the strategy to deal with them for the estimand. Estimands for the co-primary and key secondary endpoints are listed in Tables 7-2 and 7-3.

Table 7-1 List of Intercurrent Events

Intercurrent Event	Strategy to Deal With Intercurrent Event Within Analysis	Assessment of Subject
Treatment discontinuation	Treatment policy	Use observed response

This document is confidential.

Table 7-2: Estimands for Co-primary Endpoints (2 endpoints)

[figure not shown]
Endpoints	Estimands
Proportion of subjects with an IGA success (defined as an IGA of 0 [clear] or 1 [almost clear] and a \geq 2-point reduction from Baseline) at Week 16	Population: ITT population (Full population; Baseline PP NRS \geq 7)
	Endpoint: a binary response indicates if subjects have IGA of 0 [clear] or 1 [almost clear] and a \geq 2-point reduction from Baseline at Week 16
	Intercurrent events: use of rescue therapies prior to Week 16 is considered as non-responder; the observed response at Week 16 after treatment discontinuation will be used in the analysis.
	Summary measure: treatment difference of nemolizumab and placebo in response rate
Proportion of subjects with EASI-75 (\geq 75% improvement in EASI from Baseline) at Week 16	Population: ITT population (Full population; Baseline PP NRS \geq 7)
	Endpoint: a binary response indicates if subjects with at least 75% improvement in EASI from baseline at Week 16
	Intercurrent events: use of rescue therapies prior to Week 16 is considered as non-responder; the observed response at Week 16 after treatment discontinuation will be used in the analysis.
	Summary measure: treatment difference of nemolizumab and placebo in response rate

Table 7-3 Estimands for Key Secondary Endpoints (9 endpoints)

Endpoints	Estimands
Proportion of subjects with an improvement of PP NRS \geq 4 at Week 16	Population: ITT population (Full population; Baseline PP NRS \geq 7)
	Endpoint: a binary response indicates if subjects have IGA of 0 [clear] or 1 [almost clear] and a \geq 2-point reduction from Baseline at Week 16
	Intercurrent events: use of rescue therapies prior to Week 16 is considered as non-responder; the observed response at Week 16 after treatment discontinuation will be used in the analysis.
	Summary measure: treatment difference of nemolizumab and placebo in response rate
Proportion of subjects with PP NRS < 2 at Week 16	Population: ITT population (Full population; Baseline PP NRS \geq 7)
	Endpoint: a binary response indicates if subjects with PP NRS < 2 at Week 16
	Intercurrent events: use of rescue therapies prior to Week 16 is considered as non-responder; the observed response at Week 16 after treatment discontinuation will be used in the analysis.
	Summary measure: treatment difference of nemolizumab and placebo in response rate
	Population: ITT population (Full population; Baseline PP NRS \geq 7)

This document is confidential.

CCI

[figure not shown]
1.0

CD14152.SPR118169.SAP.V01

Approved 10-Nov-2022 00:00:00

This document is confidential.

CCI

1.0

CD14152.SPR118169.SAP.V01

Approved 10-Nov-2022 00:00:00

This document is confidential.

8. General Aspects for Statistical Analysis

8.1. General Methods

All data will be listed, and summary tables will be provided. Summaries will be presented for each treatment and visit (if applicable).

Unless otherwise stated, continuous variables will be summarized using the number of observations (n), mean, standard deviation (SD), median, Q1, Q3, minimum, and maximum by treatment group and visit (if applicable). Categorical variables will be summarized using frequency and percentages of subjects for each category by treatment group and visit (if applicable).

Unless otherwise stated, all statistical tests will be 2-sided and conducted at the 5% level; all presented confidence intervals (CIs) will be 2-sided 95% CIs.

8.2. Key Definitions

Screening Period is a Period of approximately 2-4 weeks before Day 1/Baseline during which subject eligibility is evaluated and standardized background topical therapy is introduced over a run-in Period of at least 2 weeks before Day 1/Baseline.

The Initial Period is defined as Day 1/Baseline to Week 16 (before the Week 16 dose, with last dose at Week 12). If early discontinued during treatment period, it is defined as the period until 4 weeks after last dosing date or early termination date whichever is earlier.

The Maintenance Period is defined as Week 16 (Maintenance Baseline) to Week 48. If early discontinued during treatment period, it is defined as the period until 4 weeks after last dosing date or early termination date whichever is earlier.

Follow-up Period is defined as the post end of treatment period (i.e., 1 day after end of treatment period) to Follow-up visit in respective treatment period.

The Baseline value of the Initial Period will be taken as latest valid value prior to first injection of study drug. For subjects randomized but not treated, the Baseline value will be the latest value prior to the randomization. Week 16 measurements will serve as Baseline measurements for the Maintenance Period (i.e., Maintenance Baseline). If Week 16 measurements are missing for re-randomized subjects, the last valid non-missing measurement in the Initial Period (i.e., before the dosing for Maintenance Period at Week 16 visit) will be taken as the Baseline measurement for the Maintenance Period.

For diary data (e.g., Peak Pruritus (PP) NRS, Sleep disturbance (SD) NRS), the Baseline values will be the weekly prorated average of non-missing subject diary scores reported during the 7 days. A minimum of 4 daily scores out of the 7 days is required to calculate the weekly prorated average score. Refer the details for the analysis visit window for diary data in Section 8.4.

The date of first treatment is defined as the date of first injection of study drug. The date of first treatment is the Baseline date.

The date of last treatment is defined as the date of last injection of study drug.

Study day is defined as the number of days from the date of first treatment and will be calculated as follows:

This document is confidential.

- If the event date \geq date of first treatment, study day = event date – date of first treatment + 1. Study Day 1 is therefore defined as the day of first treatment.
- If the event date $<$ date of first treatment, study day = event date – date of first treatment.

A subject's date of last participation in the trial is the last date of contact.

8.3. Missing Data

The data after the receipt of rescue therapy will be handled before imputation as below:

Use of rescue therapy: Except OC, all efficacy data on or after the receipt of rescue therapy will be considered as 'not evaluable data' for analysis. For analysis purpose it will be replaced by the worst possible score for endpoint, and considered as 'treatment failure'. However, in OC analysis, all observed data even after the receipt of rescue treatment will be included for analysis, i.e. no imputation for missing data.

In case of diary data, if the date of rescue therapy use is within the analysis visit window, the subject at the analysis visit will be treated as treatment failure except for OC analysis, and the weekly average will be imputed using the worst case value.

Further details for the data handling for rescue therapy are in section 7.

The primary method to impute the missing values will be as follows:

Continuous Endpoints: For continuous endpoints during Initial Period, the MI under MAR assumption approach and the MMRM approach will be used to handle the missing data for the selected secondary endpoints.

CCI

Binary Endpoints: All missing values will be treated as a non-responder for the binary endpoints for primary, key secondary and secondary endpoints during Initial Period. To assess the robustness of non-responder analysis for primary and key secondary endpoints, a tipping point analysis will be performed. The MI under MAR assumption, LOCF, and OC will be used as sensitivity analysis to impute the missing values for the primary and key secondary endpoints.

Adverse events and concomitant medications/procedures: Missing assessment times will have imputed times for the purposes of assessing treatment emergence for AEs or classifying medications/procedures into prior/concomitant. However, the assessment times (start date, stop date, and time if collected from CRF) without imputation will be presented in the listings.

For the start of a concomitant medication/procedure or AE:

- Only the year is reported: If the subject received the first study drug dose in the year reported, then the date of the first dose of study drug will be used as the start date; otherwise, January 1 of the year reported will be used as the start date.
- The month and year are reported: If the subject received the first study drug in the month and year reported, then the date of the first dose of study drug will be used as the start date; otherwise, the first day of the month and year will be used as the start date.

This document is confidential.

- The time is collected but missing: If the start date is the same as the date the subject started receiving study drug, then the time of the first dose of study drug will be used as the start time; otherwise, 00:00 will be used as the start time.

For the end of a concomitant medication/procedure or AE:

- Only the year is reported: The earlier between December 31 of the year reported and the date of the last study contact with the subject will be used as the stop date.
- The month and year are reported: The earlier between the last date of the month and year reported and the date of the final contact with the subject will be used as the stop date.
- The time is collected but missing: 23:59 (or 23:59:59 if collected up to seconds) will be used as the stop time.

If an AE has the start date completely missing and the stop date on/after the first dose date of study drug, this AE will be considered as treatment emergent (TEAE).

If a medication/procedure has the stop date completely missing, this medication/procedure will be considered as ongoing and concomitant. If the start date of a medication/procedure is completely missing and impossible to identify different by stop date, this medication will be considered as concomitant.

